With funding from a Career Development Award from the Veteran's Affairs (VA) and rigorous formative research, we developed a technology-assisted weight management intervention, called Goals for Eating and Moving (GEM). This intervention is based on the 5As framework (assess, advise, agree, assist, arrange) as recommended by the United States Preventive Services Task Force and reimbursed by the Centers for Medicare and Medicaid Services. The GEM intervention uses a tablet-delivered online tool to facilitate in-person and telephone-delivered health coaching by non-clinical staff, provide tailored patient education materials, and activate patients to set behavior change goals and discuss weight management treatments with their healthcare teams. Preliminary data suggests that the GEM intervention is feasible and acceptable to Veterans and VA staff and facilitates 5As counseling. An ongoing RCT will determine if it promotes weight loss.

The Patient-Centered Medical Home model is an expanded care model emphasizing patient-centered care delivered by inter-professional teams of individuals working to integrate evidence based approaches to improve individual and population health.^{14,15} However, it is unclear how the Patient-Centered Medical Home model can be used to address barriers to 5As implementation, improve weight management counseling, and increase participation in intensive weight management programs. We developed GEM (Goals for Eating and Moving), an innovative, technology-assisted 5As-based intervention for Medical Homes to promote weight loss, behavior change, and participation in intensive weight management programs. To establish the efficacy of the GEM intervention, we will conduct a cluster randomized controlled 12-month intervention of 16 primary care teams at two urban healthcare systems with Medical Home models of care to compare the GEM intervention (intervention arm) with Enhanced Usual Care (educational materials; control arm).

Specific Aims

1. Test the impact of the GEM intervention on weight change, and clinical and behavioral outcomes.
2. Identify predictors of weight loss in the GEM intervention arm related to: a) goal-setting processes and b) intervention components
3. Determine the impact of the GEM intervention on obesity-related counseling practices and attitudes in primary care providers.

Hypothesis

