- Participated in MOVE!, DPP, or another intensive weight management program (>4 sessions) in the past year,
- Have a history of bariatric surgery,
- Are pregnant, breastfeeding or become pregnant during the intervention period,
- Have a provider who states they should not participate,
- Have self-reported inability to read at 5th grade level.
- Currently take weight-loss medications or diabetes medication that may impact weight change
- Receive chemotherapy or cancer treatment
- Had metastatic cancer in the last 6 months
- Does not want to lose weight

We are excluding individuals with any of the above listed conditions as this will likely impact their ability to fully participate in this study. Additionally, some of these listed health conditions may limit physical activity. As this intervention includes telephone weight management counseling and reviewing of printed weight management materials, we are excluding participants without a telephone or participants who cannot read material written at the 5th grade level or above.

We will use phone screen and EHR information to verify inclusion and exclusion criteria.

Vulnerable Subjects

No vulnerable populations will be included as part of this weight management intervention study.

III. Methods and Procedures

[figure not shown]
We will conduct a cluster-randomized controlled trial of the GEM intervention at two healthcare systems in New York City: The VA New York Harbor Healthcare System (Manhattan campus) and Montefiore Medical Group (4 sites affiliated with New York City Research and Improvement Networking (NYC RING) practice-based research network. Participants will be randomized at the team level (19 teams with approximately 28 providers and 512 patients to achieve a sample size of 384 patients at 12 month follow-up for the primary outcome assessment). The primary care teams will be randomized using a random number generator (block randomization with block size of four) to either the GEM Intervention or Enhanced Usual Care arms. Randomization will be stratified by healthcare system (MMG and VA).

Intervention Arm – GEM

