Primary Care Teams: At 12 months, we will give surveys to providers, which will be administered in paper and then entered into our REDCap database. Alternatively, we will administer the provider survey online via REDCap. Furthermore, we will conduct qualitative interviews, and audiotape select visits.

Future Directions: In future versions of the GEM intervention we would like to add a visualization technique called Mental Contrasting with Implementation Intentions (MCII) that is utilized through an exercise called WOOP (Wish, Outcome, Obstacle, Plan). MCII is a novel, practical strategy that was developed and tested through 20+ years of research to promote motivation and behavior change, particularly for challenging behaviors.¹¹⁰⁻¹¹⁵ In order to obtain data on feasibility and acceptability among Veterans without introducing the burden of an additional visit, we will invite up to 20 participants in either arm at the Manhattan VA site to participate in an optional one hour session at their 24 month visit for an additional \$20. Veterans that agree to this additional session will be reconsented with the revised consent form describing this session. During this session they will receive training on WOOP and will be shown how to use the free downloadable WOOP app.²⁴ We will then ask them to share their opinions on WOOP and the app. We will not collect any information from the WOOP app and discussed this piece of the protocol with the Privacy Officers ([name] and [name]). In addition to this training, we will ask each participant a few brief questions related to goal commitment and stage of change before and after the WOOP training. We will also ask permission to follow up via telephone at 3 days and 1 month after the training to see if they have used the technique to make any changes related to weight, diet or physical activity. The materials for this session can be found in Appendix F.

Data Analysis and Data Monitoring

First, all the variables will be summarized (intention-to-treat approach) using mean (with standard deviation) and median (with interquartile range for continuous variables and frequency table for categorical variables) overall and by interventions arms, respectively. Then, Mann-Whitney tests for continuous variables and Fisher's exact tests for categorical variables will be used to check if both providers' and patients' baseline characteristics are balanced between the interventions arms.

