Impact of the GEM Intervention on obesity-related counseling practices and attitudes in primary care providers: We will use Mann-Whitney tests for continuous provider-level outcomes and Fisher's exact tests for categorical provider-level outcomes to compare the two intervention arms at each survey. Confidence intervals of the effects will also be computed.

Data Monitoring: There will be no formal data and safety monitoring board for this

protocol as there is only minimal risk associated with participation in the current study. The PI will monitor data and safety. Should unanticipated reportable events occur, defined as internal or external events (such as deaths, life-threatening experiences, injuries, breaches of confidentiality, or other problems) any time during or after the research study, which in the opinion of the PI are unanticipated, the PI will report them immediately to the NYU IRB. Any new information indicating a change to the risks or potential benefits of the research, any deviation from the protocol, and any possible serious or continued non-compliance will be reported to the NYU IRB by the principal investigator immediately.

Data Storage and Confidentiality

Storage of Subject Data: All subject data collected from the GEM online tool including survey responses and recording of responses while using the tool, interviews, focus groups, pre/post surveys, and measurements will be kept confidential and anonymous through de-identification. This signifies that subject names, dates of birth, and primary care provider names will be de-identified both in audio and written script during the transcription, segmentation, and coding process. Study session data will be entered into REDCap, which is a password-protected database. Subjects will each be given a study identification number, which will be stored in the password-protected database. Patient identifying information (e.g. subject name and date of birth) will be maintained REDCap, which is a password-protected database. All paper data will be kept in a locked, fire-proof file cabinet dedicated to the study that is kept in one of the study team's locked offices (15028BN, 15028AN 15028CN, or 15161N at the Manhattan VA).

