 - Health Coaches: Health coaching patients and data collection

VI. Subject Identification, Recruitment, and Consent/Assent

Method of Subject Identification and Recruitment

- ❖ **Primary Care Teams** – Primary care teams at each site that meet the eligibility criteria below will be separately assigned a number using a random number generator, and the first seven teams selected at each site will enroll in the study for a total of 19 primary care teams (11 VA and 8 MMG). Individual providers will be allowed to opt out of the study. We do not anticipate that providers will drop out once enrolled, based on the VA PROVE study where all 18 eligible teams and 51/52 providers participated for the duration of the study.⁶⁵ While pods (at MMG) and PACTs (at VA) have variable numbers of providers and patients, we will recruit 2-3 providers from each team prior to randomization to ensure similar numbers of teams, providers, and patients in each arm. **Table 2** (below) provides an overview of the staffing/patient population for each site.

[figure not shown]
Table 2: Description of PC staffing and patient populations at each of the VA and MMG sites (Data from the VA PC Almanac as of May 2015 or from MMG site director budget reports)

Site	#Teams (Pods or PACTs)	# Providers	Total # Patient s in PC	% Obese	% Female	% Hispanic or Latino
VA Brooklyn	12	24	13,219	32.7	11%	21%
VA Manhattan	11	28	13,813	26.7	8%	
MMG Bronx East	3	17	24,917	47.0	62%	38%
MMG Grand Concourse	2	11	17,841	41.0	67%	40%
MMG University Avenue	2	9	3,679	42.0	58%	79%
MMG Castle Hill	1	7	6,079	45.6	59%	58%

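### Aim 3 tests individual providers as independent although teams are randomised; the resulting error is modest, and the provider count and survey schedule need reconciling

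*Combined protocol and SAP*

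**What the plan says.** Under Data Analysis and Data Monitoring, the paragraph on provider counseling practices and attitudes gives the whole Aim 3 comparison: "We will use Mann-Whitney tests for continuous provider-level outcomes", Fisher's exact tests for categorical outcomes, and confidence intervals by an unnamed method. The arms are compared "to compare the two intervention arms at each survey".

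Three other places bear on this.

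- Methods and Procedures sets the unit of allocation and the numbers: "Participants will be randomized at the team level (19 teams with approximately 28 providers and 512 patients". Allocation is in blocks of four, stratified by healthcare system.
- Section VI, under Primary Care Teams, gives 11 VA and 8 Montefiore teams and says "we will recruit 2-3 providers from each team prior to randomization".
- Data Collection, under Primary Care Teams, schedules one provider survey: "At 12 months, we will give surveys to providers".

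For Aim 1, the simple tests are followed by a mixed model that allows for correlation of patients within providers. Nothing comparable follows for Aim 3.

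**The concern.** Providers in one team work with the same staff and patients and receive the same allocation. If their answers are positively correlated, a test that counts each provider as an independent observation understates the variance of the arm difference. The type I error then rises above its nominal level and intervals computed on the same basis are too short. Aim 3 is one of three specific aims, and as written no planned analysis of it respects the randomised unit.

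Two inconsistencies make the size hard to judge. The provider count determines how many providers share a team, and the plan gives two incompatible figures. The number of provider surveys also differs between the analysis text and the data collection text, so it is unclear which comparisons will be made.

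**Working it through.** **Plan's own figure.** The documents state no sample size, alpha, power or ICC for Aim 3, so there is nothing to reproduce. Two-sided 5% and an ICC of 0.1 to 0.2 are assumptions.

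**Provider count.** 28 / 19 = 1.47 providers per team. Two to three per team over 19 teams gives 19 x 2 = 38 to 19 x 3 = 57. These cannot both hold. In Table 2, 28 is also the provider count of VA Manhattan alone, which may explain the figure but does not establish it. The introduction further describes a "cluster randomized controlled 12-month intervention of 16 primary care teams", against 19 elsewhere.

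**Design effect.** DE = 1 + ((cv² + 1)m - 1) x ICC, where m is the mean and cv the coefficient of variation of team size. The term (cv² + 1)m equals the sum of squared team sizes over the number of providers. For 28 providers taken as nine teams of two and ten of one, this is (9 x 4 + 10 x 1)/28 = 46/28 = 1.643. DE is then 1 + 0.643 x 0.1 = 1.064, or 1.129 at ICC 0.2. For three per team, DE = 1 + 2 x 0.1 = 1.20, or 1.40.

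**Type I error.** The normal approximation is 2(1 - Φ(1.96/√DE)). It was checked by simulation with 8,000 runs per case, 19 teams split 9/10, normally distributed team and provider effects, and a binary outcome at about 50% for Fisher's test. Simulation standard error near 5% is √(0.05 x 0.95/8000) = 0.24 percentage points.

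| Providers | ICC | DE | Approximation | Mann-Whitney, simulated | Fisher, simulated |
|---|---|---|---|---|---|
| 28 (1.47 per team) | 0.1 | 1.064 | 5.7% | 5.7% | 2.7% |
| 28 | 0.2 | 1.129 | 6.5% | 6.0% | 2.8% |
| 38 (2 per team) | 0.1 | 1.100 | 6.2% | 6.0% | 4.4% |
| 38 | 0.2 | 1.200 | 7.4% | 6.8% | 5.3% |
| 48 (nine teams of 2, ten of 3) | 0.1 | 1.163 | 6.9% | 6.5% | 5.0% |
| 48 | 0.2 | 1.325 | 8.9% | 8.3% | 6.1% |
| 57 (3 per team) | 0.1 | 1.200 | 7.4% | 6.6% | 4.4% |
| 57 | 0.2 | 1.400 | 9.8% | 9.7% | 5.7% |

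Fisher's 5.3% at two per team is within simulation error of 5%.

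**Interval width.** A team-aware standard error is larger by √DE. Over ICC 0.1 to 0.2 this is 1.03 to 1.06 with 28 providers, 1.05 to 1.10 with 38, and 1.10 to 1.18 with 57.

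**Precision and baseline.** Ignoring clustering, 14 against 14 providers gives a standard error of √(2/14) = 0.38 SD and a detectable difference at 80% power of (1.96 + 0.84) x 0.378 = 1.06 SD. With 57 providers these are √(2/28.5) = 0.26 SD and 0.74 SD. A baseline score with an assumed correlation of 0.5 to 0.7 multiplies the detectable difference by √(1 - r²). With 28 providers, 1.06 SD becomes 0.92 to 0.76 SD.

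**Surveys.** The analysis text implies more than one provider survey; the data collection text schedules one. A balance check on providers' baseline characteristics is planned, but no baseline measure of competency or attitudes is scheduled.

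**The case against.** The best defence is that the error is small and the aim secondary. With the stated 28 providers, roughly half the teams contribute only one. Mann-Whitney inflation is then about a percentage point, and Fisher's exact test is conservative. The only stated hypothesis concerns weight loss. This stands as to size. It does not remove the mismatch, because the plan's own recruitment rule implies two to three providers per team, where the inflation is larger.

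Several stronger readings are tempting, but the documents do not support them.

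- *The lack of a baseline survey makes p-values too small or the comparison invalid.* A post-only comparison of randomised arms is valid. Chance imbalance between arms is already part of its standard error, and a baseline covariate would gain precision only.
- *There is certainly no baseline survey.* The only one scheduled is at 12 months, but the analysis wording points to more than one and the survey appendix is not in the reviewed text. What can be shown is an inconsistency.
- *High inflation and a 0.38 SD standard error apply together.* The 9.7% error belongs to 57 providers, where the standard error is 0.26 SD before clustering; 0.38 SD belongs to 28 providers.
- *All of Aim 3 rests on one survey.* Chart reviews of counseling, provider interviews and audiotaped visits are also planned. The competency and attitude items are the part tied to the survey.
- *Providers in a team share a coach.* No section assigns coaches by team. Common team membership and allocation are enough for the argument.

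It is also fair to object that a random-intercept variance is hard to estimate when many teams have one provider. That favours the permutation test.

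**Conclusion.** The concern holds in a limited form. Both Aim 3 tests ignore the team, which is the randomised unit, and no other Aim 3 analysis makes up for it. Under an assumed ICC of 0.1 to 0.2, Mann-Whitney error is about 5.7-6.0% with 28 providers, 6.0-6.8% with two per team and 6.6-9.7% with three. Fisher's exact test is clearly above 5% only towards three per team with an ICC of about 0.2 or more.

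These figures rest on the assumed ICC, equal-sized arms by team, and no difference between systems. If the systems differ, stratified allocation that the tests then ignore would pull the error the other way. If the ICC is near zero, there is no inflation. The primary weight outcome is untouched.

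The two inconsistencies stand without any assumption: one provider survey against several, and about 28 providers against 38 to 57.

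**What to change.** 1. Replace the Aim 3 tests with a permutation test that reallocates whole teams within healthcare system, following the actual randomisation. Resolution is no obstacle: each full block of four has 6 orderings, so 8 Montefiore teams give 6 x 6 = 36 allocations, 11 VA teams give 6 x 6 x 6 = 216 (the last block cut to three), and together 36 x 216 = 7,776. The alternative is a mixed model with a team random intercept, a fixed effect for system and small-sample degrees of freedom. State the confidence interval method and put it on the same basis.
2. Reconcile the number and timing of provider surveys between Data Collection and the analysis text.
3. Reconcile the provider count (about 28 against two to three in each of 19 teams) and the team count (16 against 19).
4. If a baseline provider score exists, or can still be collected before randomisation, use it as a covariate. The Future Directions text already plans reconsent at 24-month visits, which suggests that randomisation is past. In that case this item lapses and items 1 to 3 remain.

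Items 1 to 3 cost wording only. The statistical price is slightly wider intervals: about 3-6% with 28 providers and up to 10-18% with three per team, over the same ICC range. A new baseline wave would take a few minutes per provider, could slightly prime responses, and may need ethics review because completing the survey serves as consent.

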 - Health Coaches: Health coaching patients and data collection

VI. Subject Identification, Recruitment, and Consent/Assent

Method of Subject Identification and Recruitment

- ❖ **Primary Care Teams** – Primary care teams at each site that meet the eligibility criteria below will be separately assigned a number using a random number generator, and the first seven teams selected at each site will enroll in the study for a total of 19 primary care teams (11 VA and 8 MMG). Individual providers will be allowed to opt out of the study. We do not anticipate that providers will drop out once enrolled, based on the VA PROVE study where all 18 eligible teams and 51/52 providers participated for the duration of the study.⁶⁵ While pods (at MMG) and PACTs (at VA) have variable numbers of providers and patients, we will recruit 2-3 providers from each team prior to randomization to ensure similar numbers of teams, providers, and patients in each arm. **Table 2** (below) provides an overview of the staffing/patient population for each site.

[figure not shown]
Table 2: Description of PC staffing and patient populations at each of the VA and MMG sites (Data from the VA PC Almanac as of May 2015 or from MMG site director budget reports)

Site	#Teams (Pods or PACTs)	# Providers	Total # Patient s in PC	% Obese	% Female	% Hispanic or Latino
VA Brooklyn	12	24	13,219	32.7	11%	21%
VA Manhattan	11	28	13,813	26.7	8%	
MMG Bronx East	3	17	24,917	47.0	62%	38%
MMG Grand Concourse	2	11	17,841	41.0	67%	40%
MMG University Avenue	2	9	3,679	42.0	58%	79%
MMG Castle Hill	1	7	6,079	45.6	59%	58%

❖ **Patient Recruitment (Figure 2 below)** – Using the Patients Health Information Systems and Technology Architecture (VistA), the VA's Health Information Technology system, and the Montefiore EPIC and Clinical Looking Glass systems, we will identify patients with upcoming primary care appointments who meet the eligibility criteria. A Research Assistant (RA) will confirm eligibility by EHR and provider review. One to two weeks before their baseline visit, eligible participants will be sent a letter signed by both the Principal Investigator (PI) and giving them the opportunity to opt out (i.e., request to not be contacted). The RA will call patients to recruit, screen for eligibility, and schedule the baseline. This allows enough time for all intervention components to be completed, and is responsive to patient scheduling preferences expressed in a similar recruitment strategy used in the VA PROVE study⁶⁵ and our pilot studies.

Eligibility will be based on the inclusion and exclusion criteria established for the study. Participation in the study is completely voluntary and all prospective subjects may refuse to participate or withdraw from the study at any given time.

Figure 2: Recruitment and Eligibility Screening

Process of Consent

Consent will be obtained by a research assistant trained in consenting protocols. Once subjects have been identified as eligible, the study will be described in detail and informed consent will be obtained from subjects who wish to participate. An audio-video consent form will also be described in detail for subjects who agree to have their study session audio recorded.

Subject Capacity

In order for subjects to be eligible to participate in the study, subjects must have the capacity to give informed consent. Capacity will be assessed with the set of inclusion and exclusion criteria that has been established specifically for this study. In short, participants must be at least 18 years of age, have access to a telephone, be able to travel for in-person evaluations, and not currently have functional impairments that limit

physical activity.

Subject/Representative Comprehension

Research Assistants will be intensively trained in consenting protocols. RAs will assess comprehension by asking the subject whether the explanation of the information presented was understandable. The research assistant will be prepared to clearly summarize each section and will answer questions the subject may have about the consent forms. A copy of the consent form will be available for the patient to take home with them or will be sent to them.

Debriefing Procedures

For this particular weight management intervention study, no information will be purposely withheld from any of the subjects who are recruited and/or are actively enrolled in the study.

Consent Forms

For the patient participants, two consent forms will be used: the research subject informed consent and audio-video consent forms. For provider participants, completion of the survey will serve as implied consent. On the first page of the survey, it will explicitly state that participation is voluntary and that completion serves as consent. A waiver of documentation of informed consent was requested for the provider survey. For provider participants, who chose to participate in qualitative interviews, we have a separate research subject informed consent form.

Documentation of Consent

Written consent will be obtained from all patient subjects who are eligible and agree to participate in the study and for provider subjects who chose to participate in qualitative interviews. Documentation of consent will be securely stored in the research team's locked office on 15 North (15028CN) at the Manhattan VA Hospital.

Costs to the Subject

There will be no costs to the subjects for participating in this study. However, medical care and services provided by subjects' current health care facility that are not part of the study, which includes normal visits and prescription expenses, may require payment.

Payment for Participation

To compensate for travel and time spent completing survey measures and basic measurements, study participants will be given cash or a ClinCard in the amount of 25 dollars for the Baseline study visit, 30 dollars for the 6 month visit, 40 for the 12 month visit, and 50 dollars for the 24 month study visit and 20 dollars for the optional opinion session at the same 24 month study visit for up to a subset of 20 participants. This proposed payment is reasonable and commensurate with the expected contributions of participants and is meant to provide additional incentives for participants to complete all 4 study visits. This amount of payment and the terms of the payment are included in the informed consent form. This payment is fair and appropriate and does not constitute

undue pressure or influence, or coercion of, the prospective research participant to volunteer for or continue participation in the research study.

VII. List of Appendices

1. Appendix A - Recruitment Protocols and Materials*
2. Appendix B – Data Collection Surveys*
3. Appendix C - GEM Online Tool Screenshots*
4. Appendix D – GEM Personalized Binder Materials
5. Appendix E - Health Coaching Training Materials and Protocols*
6. Appendix F – WOOP Materials

VIII. Bibliography

doi:10.1007/s11606-010-1279-z.
doi:10.1056/NEJMoa012512.
doi:10.1038/oby.2010.273.

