The patients within primary care teams randomized to the Goals for Eating and Moving (GEM) intervention will have greater weight loss than those who receive Enhanced Usual Care.

Research Design

- a. We will conduct a cluster-randomized controlled trial of the GEM intervention at two healthcare systems in New York City: The VA New York Harbor Healthcare System (Manhattan campus) and Montefiore Medical Groups (4 sites affiliated with New York City Research and Improvement Networking practice-based research network).
- b. We will conduct a RE-AIM (reach, efficacy, adoption, implementation, and maintenance) evaluation of the GEM intervention.²⁰
- c. We will explore potential effects of secondary measures such as perceived procedural fairness or experiences of discrimination on health outcomes and weight-loss behaviors including but not limited to dietary behaviors, physical activity, and quality of life measures.

Background

Modest weight loss (7%) via the Diabetes Prevention Program (DPP) can reduce the risk of diabetes in high-risk patients by 58%.³ Similarly, all Veterans Affairs (VA) Medical Centers offer the MOVE! program, a lifestyle-based program delivered in small group sessions.^{4, 26, 27} One report found that patients who attended two or more MOVE! sessions were more likely than matched controls to have clinically significant (>5%) weight loss and less likely to gain weight.²⁸ Unfortunately, intensive lifestyle programs like this are not available to most primary care patients and very few studies have looked at interventions to treat obesity in the primary care setting,²⁹⁻³⁰ despite the obvious need for improving delivery of obesity care. We need to test more robust strategies to increase participation in these effective programs.

The primary care setting is critical to reducing the burden of obesity. Primary care (PC) is an important venue to promote weight loss through lifestyle behavior change, and effective PC-based interventions can potentially have a significant public health impact,

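### The protocol gives both 16 and 19 teams, its seven-per-site rule yields neither, and about 28 providers is too few for two to three per team

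*Combined protocol and SAP*

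**What the plan says.** The opening summary, before the Specific Aims, describes a cluster-randomised "intervention of 16 primary care teams at two urban healthcare systems". Section III, Methods and Procedures, states that "Participants will be randomized at the team level" and gives the size as "19 teams with approximately 28 providers and 512 patients". Section VI, under Primary Care Teams, says that "the first seven teams selected at each site will enroll in the study for a total of 19 primary care teams", and its parenthesis splits the 19 into 11 at the VA and 8 at MMG.

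Research Design names the sites as the Manhattan campus of the VA system and "Montefiore Medical Groups (4 sites affiliated with New York City Research and Improvement Networking practice-based research network". Table 2 lists 11 teams and 28 providers at VA Manhattan, and 3, 2, 2 and 1 teams at the four MMG clinics. It also lists VA Brooklyn, which is not a named study site.

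On providers, section VI says "we will recruit 2-3 providers from each team prior to randomization" and lets individual providers opt out, without giving a rate. For the provider-level outcomes, the analysis section says "We will use Mann-Whitney tests for continuous provider-level outcomes". The mixed model for patient outcomes accounts for correlation among patients of the same provider.

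**The concern.** The team is the randomised unit, so the number of teams is a basic sample-size figure, yet two values appear in the current text. The selection rule contradicts the total in its own sentence: staff who stop at seven per site cannot enrol 11 VA teams, and staff who enrol 11 have not followed the rule. The provider total in the Methods falls below the minimum set by the recruitment rule. Providers are the unit of the provider-level analyses and a clustering level in the mixed model, so both need a provider count that can be relied on. Left as it stands, a final report could not say against which plan the enrolment of teams and providers should be judged.

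**Working it through.** **Inputs.** Team counts: 16 (opening summary), 19 (section III), 19 = 11 + 8 (section VI). Selection rule: seven teams per site (section VI). Teams and providers by clinic: Table 2. Provider total: about 28 (section III). Providers per team: 2 to 3 (section VI). Patients: 512 enrolled, 384 completing, 75% retention (section II).

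**Figures that reproduce.**
- Patients: 384 / 0.75 = 512.
- Teams: 11 + (3 + 2 + 2 + 1) = 11 + 8 = 19. So 19 is every team listed at VA Manhattan and the four MMG clinics.

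**The seven-per-site rule.**
- Site means healthcare system: 7 + 7 = 14.
- Site means clinic: 7 + 3 + 2 + 2 + 1 = 15, since no MMG clinic has as many as seven teams.
- Bringing in VA Brooklyn or ignoring the available numbers does not help:
  - two VA campuses plus MMG as one site: 3 × 7 = 21
  - six clinics limited to available teams: 7 + 7 + 3 + 2 + 2 + 1 = 22
  - five clinics unlimited: 5 × 7 = 35
  - six clinics unlimited: 6 × 7 = 42

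No reading gives 16 or 19.

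**Providers.**
- Minimum with 19 teams: 19 × 2 = 38. Minimum with 16 teams: 16 × 2 = 32.
- Stated total per team: 28 / 19 = 1.47, or 28 / 16 = 1.75. Both are below two.
- Shortfall against the minimum for 19 teams: 38 − 28 = 10, and 10 / 38 = 26%.
- Patients per provider: 512 / 28 = 18.3, against 512 / 38 = 13.5.
- Table 2 lists exactly 28 providers at VA Manhattan alone, and 14 × 2 is also 28. The stated figure may therefore be a VA-only count or left over from a 14-team plan. This is inference; the documents do not say so.

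**Effect of 16 against 19 teams on the primary comparison.** The documents state no ICC, SD or power, so this is a sensitivity check on assumed values: N = 384 completers, 80% power, two-sided 5%, ICC 0.01 to 0.05, equal team sizes. The detectable difference in SD units is (t0.975 + t0.80 on K − 2 df) × 2 × √{[1 + (N/K − 1) × ICC] / N}.

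| Teams (K) | Completers per team | ICC 0.01 | ICC 0.05 |
|---|---|---|---|
| 16 | 24.0 | 0.341 | 0.451 |
| 19 | 20.2 | 0.331 | 0.425 |
| Ratio, 16 to 19 | | 1.029 | 1.061 |

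**The case against.** The working team count is not in serious doubt. The Methods and the recruitment section both say 19, the latter gives the split, and Table 2 supports it. The 16 appears once, in an introductory summary, and the seven-per-site wording looks left over. That is fair, and it makes this part an editorial correction. Even so, the faulty rule sits in the same sentence as the total it contradicts, so the reader has to work out which to discard.

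Opt-out might explain the provider gap. It is allowed, no rate is stated, and so it cannot be ruled out. A reader might set the 26% against the earlier VA study, in which "all 18 eligible teams and 51/52 providers participated for the duration of the study". That figure is cited to support low drop-out after enrolment; it does not measure opt-out beforehand and should not be used for this purpose.

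Three stronger readings are tempting, and the documents do not support them.
- **The provider analyses are underpowered at 28.** The Methods do not tie 28 to those analyses, and no sample size is stated for them. Any loss computed at 28 assumes that 28 is the true target, besides an assumed ICC.
- **The provider total has a firm ceiling.** Plain multiplication gives 19 × 3 = 57. Limiting VA Manhattan to its 28 listed providers gives 28 + 8 × 3 = 52. That limit applies to the whole site, and Table 2 gives no providers per team. Only the minimum of 38 is needed here.
- **Enrolling all 19 teams undermines the randomisation.** If Table 2 is current and every listed team is eligible, the random selection step chooses nothing. Allocation to arms is a separate step, stratified by healthcare system in blocks of four, and is unaffected.

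**Conclusion.** The point holds as three inconsistencies in the current text: 16 against 19 teams; a rule that gives 14 or 15 for the named sites against its own total of 19; and about 28 providers against a minimum of 38, or 32 with 16 teams. These follow from counting alone and rest on no statistical assumption. The 15 additionally relies on the Table 2 team counts, which for the VA date from May 2015.

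The consequence for the primary comparison is modest: a detectable difference about 3% to 6% larger with 16 teams than with 19, at assumed ICCs of 0.01 to 0.05. A reader might infer a material loss of power for the primary or provider outcomes. The documents give no ICC, SD or power from which to show one, so it should not be claimed. The case for correction is that the enrolment rule cannot be followed as written and that the provider total contradicts the rule meant to produce it.

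**What to change.** 1. State one team count in the opening summary, section III and section VI. The documents support 19 (11 VA, 8 MMG), for the sponsor to confirm.
2. Delete or correct the seven-per-site rule. If 19 is confirmed, say that all eligible teams at VA Manhattan and the four MMG clinics are invited.
3. Restate the provider total in section III so that it agrees with the per-team rule in section VI. If opt-out is expected to lower the total, give the assumed rate. If 28 refers to the VA alone, say so and add the MMG number.
4. Use that same total wherever the provider-level analyses are described.

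The cost is a wording amendment. It adds no patients, visits or procedures.
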